### ***Statistical Analysis***

Normality will be verified using Shapiro-Wilk tests. Normally distributed baseline characteristics will be reported as frequencies and mean standard deviation. Two-way repeated measures analysis of variance (ANOVA) models will be used to assess changes in functional connectivity between baseline, the early phase (0-15 min) of the infusion, and the late phase (15-30min) of the infusion with and without furosemide prior. If data are non-normally distributed, aligned rank transformations (ARTs) will be conducted prior to performing two-way repeated measures ANOVAs. ARTs will be completed using ARTTool2 (version 2.2.2) or ARTTool integrated into R. Significant main effects of time and time\*sex interactions will be followed with pairwise post-hoc comparisons corrected for multiple comparisons.

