### VISITS 3 & 4: fMRI SCAN (2 hours/visit; CBBI)

Subjects will be asked to log food and water intake for the 3 days leading up to the MRI visits on the AHA Sodium Tracker. Subjects will be asked to consume a diet containing 2,300 mg of sodium each of these days. Subjects will consume their own food. Food will NOT be provided by the dietitian for the 3 days leading up to the MRI visits. Subjects will be instructed to refrain from taking over the counter medications for 48 hours, and from vigorous aerobic exercise or alcohol for 24 hours prior to MRI scans. Subjects will come into the study visit after at least a four-hour fast. The MRI studies must be completed within 3 months of the screening. If we are unable to schedule both MRI visits within 3 months of screening, subjects will be asked to come to the Cardiovascular Physiology Lab again before the MRI visit for a blood draw to check if electrolyte levels are normal. The second MRI data collection must be performed no sooner than 1 week from the first MRI data collection.

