### ***Furosemide Administration***

Each subject will undergo two separate MRI study visits (visit 3 and visit 4), one with and one without NKCC2 antagonism. Furosemide (NKCC2 antagonist) will be purchased through the Nurse Managed Primary Care Center from Heritage Pharmaceuticals through McKesson ([link here](#)). NKCC2 antagonism will be achieved by administering a bolus of furosemide (40mg in 4mL of 0.9% NaCl isotonic saline) over a 2-minute period immediately prior to the hypertonic saline infusion. This timing will achieve peak NKCC2 blockade. A bolus of 0.9% NaCl (4mL) will be administered over a 2-minute period during the control infusion, and the participant will be blinded to the condition. A registered nurse, under the off-site supervision of a cardiologist will administer the bolus of furosemide and administer the hypertonic saline infusion.

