## **MRI ACQUISITION AND ANALYSIS AND STATISTICS**

### ***MRI Acquisition***

We will use a 3T MRI Siemens Prisma Scanner and 64-channel head coil to obtain all brain images. Padding will be placed around the participant's head to minimize head motion. Participants will be instructed to keep both their head and the rest of their body as still as possible.

All participants will undergo a T1-weighted anatomical scan [repetition time (TR) = 2080 ms; echo time (TE) = 4.6 ms; field of view = 210 x 210 mm; voxel size = 0.7 mm^3; slice thickness = 0.7 mm] followed by two BOLD fMRI scans (baseline & infusion). Functional scans will be acquired using a multi-band gradient-echo echo-planar imaging (EPI) sequence [TR = 829 ms; TE = 40 ms; flip angle = 52°; field of view = 208 x 208 mm; voxel size = 2.0 mm^3; slice thickness = 2.0 mm]. During functional scans, participants will be instructed to keep their eyes open and fixated on a white cross (on a black screen) to minimize the effects of eye motion and ensure the reliability and consistency of our results. These sequences are identical to those used in our group's pilot study.

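### The furosemide comparison spans two MRI visits, but the planned connectivity ANOVA has no visit term; if infusion order varies between people, adding visit and visit-by-time is a minor, cheap improvement

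*Combined protocol and SAP*

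**What the plan says.** All references are to the combined protocol and SAP.

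- **Furosemide Administration:** "Each subject will undergo two separate MRI study visits (visit 3 and visit 4), one with and one without NKCC2 antagonism". On masking, "the participant will be blinded to the condition".
- **Visits 3 & 4:** "The second MRI data collection must be performed no sooner than 1 week from the first MRI data collection".
- **MRI Acquisition:** at each visit the anatomical scan is "followed by two BOLD fMRI scans (baseline & infusion"), so each condition has a baseline from the same visit.
- **Statistical Analysis:** "Two-way repeated measures analysis of variance (ANOVA) models will be used to assess changes in functional connectivity" across baseline, the early phase and the "late phase (15-30min) of the infusion with and without furosemide prior". For non-normal data, "aligned rank transformations (ARTs) will be conducted prior to performing two-way repeated measures ANOVAs". On follow-up, significant time effects and time-by-sex "interactions will be followed with pairwise post-hoc comparisons corrected for multiple comparisons".

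The section names no visit, period or order term. It also names no follow-up of condition or condition-by-time.

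**The concern.** Within each person, furosemide versus control is also a first-session versus second-session contrast. If connectivity differs between sessions for any other reason, such as familiarity with the scanner, a model without a visit term has only two places to put that difference. With uneven orders, part of it enters the furosemide estimate. With even orders, it enters the error term. Equal numbers in each order at enrolment need not survive to analysis, because the Furosemide risk section ends a visit when a participant leaves the scanner. At stake are the error rate of the furosemide test if the analysed split is uneven, and a little power if it is even.

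**Working it through.** **Inputs.** From the documents: 50 recruited (Study Population and Recruitment), two visits, three time points. The documents give no alpha, SD, visit effect or dropout rate, and the available text gives no order split. Assumed: alpha 0.05 two-sided; 50 people with both scans; visit effect 0.3 SD (range 0.2-0.4); no true furosemide effect for error rates and a 0.4 SD effect for power; correlation across time points of the furosemide-minus-control difference 0 to 0.5. There is no figure in the plan to reproduce.

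**Bias.** Let p be the share of analysed participants with control first and v the second-minus-first visit shift. Without a visit term the condition estimate is biased by (2p - 1) x v:

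- 25:25: (2 x 0.5 - 1) x 0.3 = 0
- 30:20: (2 x 0.6 - 1) x 0.3 = 0.06 SD
- 35:15: (2 x 0.7 - 1) x 0.3 = 0.12 SD

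For condition-by-time, a shift common to all scans of a visit cancels. Simulation gives 4.9-5.0% false positives at all three splits under a constant shift. Only a visit effect that differs between baseline and infusion does harm.

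**False-positive rates by simulation, v = 0.3.** The visit effect is on the early and late phases only for condition-by-time, and is constant for the main effect.

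| Order split | Condition-by-time, no visit terms (correlation 0 to 0.5) | Main effect, no visit term | With visit terms |
|---|---|---|---|
| 25:25 | 4-5% | 4% | 5% |
| 30:20 | 5-6% | 6% | 5% |
| 35:15 | 8-11% | 12% | 5% |

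For v from 0.2 to 0.4, condition-by-time at 35:15 with zero correlation runs from 6.3% to 10.6%. The main-effect column is in SDs of the person-level difference, and the condition-by-time column in SDs of the difference at each time point, so the two are not on one scale.

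An aligned-rank run on skewed data at 35:15 (v = 0.3, sex not included) gave 8.3% without the order factor and 4.9% with it.

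**How likely is an uneven split?** Exact binomial, n = 50, probability 0.5, two-sided: 30:20 or worse, 20%; 35:15 or worse, 0.7%. Averaged over simple 1:1 randomisation, the main-effect rate without a visit term is 4.9-5.0%.

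**Power at 25:25, true effect 0.4 SD, v = 0.3, without and with the terms.** Main effect 76% and 79%. Condition-by-time 50% and 52% at zero correlation, 80% and 82% at 0.5 (on rounded figures).

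**Cost when there is no visit effect.** The variance of the furosemide estimate is multiplied by 1/(4p(1 - p)):

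- 25:25: 1/(4 x 0.5 x 0.5) = 1.00
- 30:20: 1/(4 x 0.6 x 0.4) = 1.04
- 35:15: 1/(4 x 0.7 x 0.3) = 1.19

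Power for a 0.4 SD effect then falls by about 1-2 points at 30:20. At 35:15 it falls by about 7 points: 79% to 72% for the main effect, and 52% to 45% for condition-by-time at zero correlation.

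**Can the terms be fitted?** The columns are subject 50, condition 1, time 2, condition-by-time 2, visit 1 and visit-by-time 2, total 58. At 35:15 the rank is 58. If everyone has the same order the rank is 55: the three visit columns are aliased with condition and condition-by-time.

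**The case against.** **The point may not apply.** The model is called two-way, and the only interaction named is time-by-sex. If the plan means a time-by-sex model for each condition, there is no furosemide contrast for a visit term to enter. This stands, and the point is conditional on it.

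**The harm is small and rests on assumptions.** No visit effect is given, the test that matters is immune to a constant shift, and 30:20 costs at most about one point. The documents do not suggest that scans would be lost mainly from one order: the urge to urinate arises at the furosemide visit whichever comes first. This also stands, and it is why the point is minor.

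**Adjustment is not free.** With an uneven split and no visit effect, the terms lose power. This is true, but the loss is only 1-2 points at 30:20, and the larger loss needs an unlikely split.

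**Stronger readings a reader might infer.** One is that infusion order is unplanned or not randomised, since the available text uses randomised only for the optional diets. The documents do not support this: the study design refers to Figure 1, which is not shown and may give the order. Another is that the 12% main-effect rate measures the damage to the trial. It does not: the main effect averages in the pre-infusion baseline scan, and that rate needs a split of low probability under randomisation.

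**Conclusion.** The point holds as a minor improvement. The furosemide comparison spans two visits, and the written ANOVA has no visit term. If condition is a factor and order varies between people, omitting visit and visit-by-time leaves the condition-by-time test close to 5% at likely splits. The rate reaches 8-11% only at 35:15, given a 0.3 SD visit effect confined to the infusion phases. With balanced order nothing is biased; the test is slightly conservative and forgoes about 1-3 points of power. All sizes rest on the assumed visit effect, the assumed correlation and 50 complete pairs. If the order is the same for everyone, no model term separates visit from furosemide, and the point becomes one of reporting. Neither case shows an error that invalidates the plan.

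**What to change.** 1. State whether condition is a factor in the ANOVA, and name condition-by-time as the test of furosemide.
2. If order varies between people, fit condition, time, condition-by-time, visit and visit-by-time, with sex and time-by-sex as planned. In a repeated measures ANOVA, add order group (control first or furosemide first) as a between-person factor: condition-by-order is then the visit effect, and condition-by-order-by-time is visit-by-time.
3. Use Type III tests, which weight the two orders equally. Testing condition sequentially before order keeps the bias: 13.2% for the main effect at 35:15 with v = 0.3.
4. Use the same factor in the aligned-rank version.
5. Report the order split among those with both scans.
6. If the order is fixed, say in the report that visit and furosemide effects cannot be separated.

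Cost: analysis only, with no extra visits or participants. At n = 50, before any sex terms, error degrees of freedom fall from 49 to 48 for condition and from 98 to 96 for condition-by-time. The remaining cost is the variance inflation shown above when the split is uneven.

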### **Furosemide**

There are several risks of infusing furosemide although the adverse reactions are uncommon. Furosemide is a widely used medication. References 1 (n=199) & 3 (n=8) below used an identical dosage that we propose (40mg). The infusion of furosemide could lead to gastrointestinal, allergic, central nervous system, blood and heart reactions. Blood pressure may decrease after the furosemide bolus. If blood pressure goes below 90/50 mmHg after furosemide is given, we will stop the study visit. Symptomatic hypotension leading to dizziness or fainting may also result. Furosemide is a diuretic and increases the urge to urinate and can make participants feel thirsty. Because of this, it is likely that participants will need to use the restroom during the MRI scan. When subjects need to use the restroom during the MRI scan, they will be asked urinate into the absorbent brief they will be wearing. This is a normal response, but it may cause a feeling of embarrassment. If participants choose to come out of the MRI scan to use the restroom, the study will be concluded because the effect of the hypertonic saline and furosemide will have worn off by the time the participant is put back into the MRI. Participants will still be compensated and allowed to proceed with the other study visits.

Pregnancy: Furosemide falls under Pregnancy Category C. At higher than maximal recommended human doses, rodent studies have shown unexplained fetal harm. There are no adequate and well-controlled studies in pregnant women. Although there are no established guidelines at this time regarding furosemide and pregnancy, participants will be informed that there is risk. If the participant may be pregnant or if the participant does not want to expose themselves to this risk, they will be excluded from participating in this study. Female subjects will only be permitted to participate upon a negative pregnancy test.

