### ***MRI Analysis***

The preprocessing steps described here were also utilized in our group's pilot study. Functional MRI images will be converted and analyzed using several software packages including MRIcroGL, AFNI (Analysis of Functional NeurolImages) and FSL (FMRIB Software Library). Initially, the 30-minute infusion fMRI scans will be split into an early phase (0-15 minutes) and late phase (15-30 minutes). Processing steps include: 1) despiking of the resting-state fMRI scans to eliminate outliers, 2) slice-timing correction of the fMRI scans, 3) 3D rigid motion correction to a reference frame to correct for head motion in the resting-state data (we removed time points with head motion > 0.5 mm), 4) cleaning the fMRI data using ANATICOR (accounting for the 6 motion parameters, white matter, and CSF signal), 5) band-pass filtering (0.008 to 0.10 Hz) (42), 6) skull-stripping of the T1-anatomical scan using FSL, 7) co-registration (i.e., alignment) of the T1-anatomical and functional scans, 8) normalization of all scans to the 1mm MNI152 template, and 9) spatial smoothing of the resting-state data using a Gaussian kernel of full-width half maximum (FWHM) = 4mm. These smoothing dimensions align with recommendations to choose a Gaussian kernel of FWHM double the voxel size (which was 2 mm^3 for this study) and are appropriate for smaller brain structures like the SFO and OVLT.

The ROIs for this study will be defined as follows. The SFO and OVLT will be defined as a 2-mm radius spheres based on previous studies. The Montreal Neurological Institute

(MNI) coordinates corresponding to the center of each ROI are: SFO: x = 0 mm, y = 2 mm, z = -6 mm and OVLT: x = 0 mm, y = 2 mm, z = -12 mm. The location of these seeds has been verified using Duvernoy's Atlas of the Human Brainstem and Cerebellum and these ROIs are consistent with those used in a pilot study conducted in our lab.

Following pre-processing, we will conduct seed-to-seed functional connectivity analyses to assess the synchronization of the spontaneous low frequency fluctuations in the BOLD signal between our ROIs. We will calculate functional connectivity between the SFO and OVLT. Pearson correlations will be computed between the ROIs for the seed-to-seed functional connectivity analysis. Pearson correlations will be converted to Z-scores using a Fisher's transform which will be statistically analyzed, as in our pilot study.

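### The planned repeated-measures ANOVA has no rule for scans that end early; a mixed model with a preset minimum phase length would keep the usable phases at little cost

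*Combined protocol and SAP*

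**What the plan says.** **Analysis.** Under Statistical Analysis, "Two-way repeated measures analysis of variance (ANOVA) models will be used to assess changes in functional connectivity" across baseline, early and late infusion, with and without furosemide. If the data are not normal, "aligned rank transformations (ARTs) will be conducted prior to performing two-way repeated measures ANOVAs". The follow-up is described for time and time-by-sex terms: significant "interactions will be followed with pairwise post-hoc comparisons corrected for multiple comparisons". Neither this section nor any other names an analysis set, a missing-phase rule, imputation or a mixed model.

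**Phases.** Under MRI Analysis, "the 30-minute infusion fMRI scans will be split into an early phase (0-15 minutes) and late phase (15-30 minutes". Time points with head motion above 0.5 mm are removed. No minimum usable length per phase is set.

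**Early ends.** The Furosemide section under Risks and Benefits states: "If participants choose to come out of the MRI scan to use the restroom, the study will be concluded". The reason given is "because the effect of the hypertonic saline and furosemide will have worn off by the time the participant is put back into the MRI", so the session is not resumed. It then adds: "Participants will still be compensated and allowed to proceed with the other study visits". The same section stops the visit if blood pressure falls below 90/50 mmHg after furosemide. The Hypertonic Saline Infusion section under Risks and Benefits stops the infusion above 170/90 mmHg. The MRI Scan paragraph lets a participant stop whenever they wish.

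**Prevention.** Participants who need to urinate during the scan wear a brief, and "they will be asked urinate into the absorbent brief they will be wearing". Men may choose a condom catheter instead. No expected rate of early ends is given.

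**The concern.** The protocol foresees people with some phases observed and others not. A classical repeated-measures ANOVA needs every cell, so in its usual form it drops anyone with a gap. Suppose a participant stops after minute 15 of the furosemide infusion and the shortened late phase is not used. Five of that person's six cells are then complete, including everything the early-phase comparison needs, and all five would leave a condition-by-phase model.

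The plan can also be read as time-by-sex models within each condition, because those are the only follow-ups it names. The same stop would then remove two completed furosemide cells and leave the control visit untouched. A stop before minute 15 is also possible, since furosemide is given just before the infusion; that loses both infusion phases.

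At stake is mainly precision, and secondarily bias if those who stop differ in connectivity.

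**Working it through.** The plan has no power, SD or dropout figure to reproduce. The check below compares complete cases with all observed phases.

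**Inputs from the documents:** N = 50 (Study Population and Recruitment); 2 visits x 3 phases = 6 cells.

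**Assumed inputs:**
- Fraction f losing furosemide phases: 5/10/20/30%, leaving 47.5/45/40/35 complete.
- Variance 1 per cell. Within-visit correlations are listed as baseline-early/baseline-late/early-late.
- Pattern A: 0.3 between visits for every pair of phases; within visit 0.5/0.5/0.5 to 0.7/0.7/0.7, including 0.5/0.5/0.7 and 0.7/0.5/0.7.
- Pattern B: between visits 0.4 for the same phase and 0.2 for different phases; within visit all equal, 0.5 to 0.7.

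**Contrasts.** Early = furosemide (early - baseline) minus control (early - baseline). Late is defined in the same way.

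**Formulas.** With cell covariance V and contrast c:
- Complete cases: variance = c'Vc / [N(1-f)].
- All observed phases (generalised least squares): information I = sum over missingness patterns of n_p Z_p' V_p^-1 Z_p; variance = c' I^-1 c.
- SE ratio = square root of the first variance over the second.

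Two cases have a closed form:
- Only the late phase lost, early contrast: everyone has the four cells needed, so the ratio is 1/sqrt(1-f) = 1.026/1.054/1.118/1.195, whatever the correlations.
- Whole furosemide visit lost, pattern A: the two visits' changes are uncorrelated, so the ratio is sqrt[2/(2-f)] = 1.013/1.026/1.054/1.085.

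**Extra complete-case SE (%) at f = 5/10/20/30%, condition-by-phase reading:**

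| Lost in furosemide visit | Contrast | Pattern A | Pattern B |
|---|---|---|---|
| Late | Early | 3/5/12/20 | 3/5/12/20 |
| Late | Late | 2/3-4/7-9/11-14 | 1/2-3/4-6/7-9 |
| Early and late | Either | 2/3/6-7/10-11 | 1/1-2/3-5/4-8 |
| Whole visit | Either | 1/3/5/8 | 0-1/1-2/2-3/3-5 |

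These are illustrations, not bounds. Pattern B with 0.7/0.5/0.7 within visit (a nearly singular matrix) gives about 10% and 16% for the late contrast at 20% and 30% late-phase loss.

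**Time-by-sex reading, furosemide visit alone:** late phase lost, early contrast 3/5/12/20 and late contrast 1/1-3/3-6/5-9; both infusion phases lost, 0-1/1/2-3/2-4; whole visit lost, none.

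**Completed phases discarded** when only the late phase is lost (condition-by-phase): at 10/20/30%, 5/10/15 people x 5 cells = 25/50/75.

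**Bias under two hypothetical mechanisms** (probit stopping, slope 1 per SD, pattern A). The completers' mean of the value that drives stopping shifts by m = phi(k)/[sqrt(2)(1-f)], k = z(1-f), giving m = 0.077/0.138/0.247/0.351 SD.
- *Stopping depends on the observed early value.* Complete-case early bias = (1 - baseline-early correlation) x m. With correlations 0.7 to 0.5 this is 0.02-0.04/0.04-0.07/0.07-0.12/0.11-0.18 SD. An unstructured likelihood model has about 0 (1,000,000 simulated people per setting).
- *Stopping depends on the unseen late value.* At 10% and 30% loss, the late-contrast bias is 0.06-0.07 and 0.14-0.18 SD for complete cases. For the unstructured model it is 0.07-0.08 and about 0.2 SD.

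For scale, the contrast SE with nobody lost under pattern A is sqrt[4(1-r)/50], where r is the baseline-to-phase correlation: 0.200 SD at r = 0.5 and 0.155 SD at r = 0.7.

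**Feasibility at n = 50.** Unstructured REML converged in 3,600 of 3,600 simulated trials with cell means only. Mean type I error was 5.3% (early) and 5.1% (late), against 5.0% and 4.6% for complete cases. With sex terms added, the unstructured and random-effects models each converged in 120 of 120.

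**The case against.** **The empty cell is itself an assumption.** MRI Analysis computes a correlation from whatever time points survive motion removal, so phases of unequal length are already normal. A stop at minute 25 leaves 10 minutes of late-phase data and a computable value. This stands: the loss after minute 15 is conditional, and a remedy must define a usable phase.

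**Complete-case fitting is not stated.** A reader might infer that the plan deletes these participants. It does not say so; that is only how the named method usually behaves. The post-hoc pairs are not restricted to six-cell completers either, so a baseline-early pair could use everyone who has both values.

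**Stops may be rare.** Briefs, condom catheters and screening are meant to keep them few. The 20% and 30% rates have no basis in the documents, and near 5% the loss is small. This stands and limits the importance of the point.

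**A mixed model is not always better.** If stopping depends on the unseen late value, its late contrast can be somewhat more biased, and its type I error is no better. This also stands, and is why a shift analysis belongs in the plan.

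**A stronger reading to resist.** Because furosemide increases the urge to urinate, a reader might infer that the furosemide comparison will be biased. Uneven loss between conditions is plausible, but nothing in the documents links leaving the scanner to connectivity. Nor does the rule ending the session say that data already acquired are discarded, or that the person leaves the trial.

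One sentence on missing phases would close the bare gap. It would not recover the completed phases unless the method changed too.

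**Conclusion.** The point holds in conditional form, with medium confidence. The plan anticipates partial sessions and names a method that, as usually fitted, cannot use them.

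The firmest figure is the early-contrast loss when only the late phase is missing: it does not depend on the correlations and is the same under both readings of the model. The other losses are smaller and vary with correlations that the documents do not give. Across patterns A and B, they are about 1-2/2-4/4-9/7-14% for the late contrast with the late phase lost. They are about 1-2/1-3/3-7/4-11% with both infusion phases lost, and 0-1/1-3/2-5/3-8% with the whole visit lost.

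All of this rests on complete-case fitting, an unusable truncated phase and assumed stop rates. The bias figures describe hypothetical mechanisms only. The change is worth making because it costs little, not because the planned analysis is invalid.

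**What to change.** In Statistical Analysis:

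- **Model.** Replace the ANOVA with a REML linear mixed model (Kenward-Roger degrees of freedom) on all usable phase-level Fisher z values, with condition, phase, condition-by-phase and the planned sex terms. Keep people who have one visit or only some phases. If time-by-sex within condition was intended, say so and fit the same kind of model per condition on its three cells.
- **Covariance.** Unstructured as primary, with person plus person-by-visit random effects as the pre-stated fallback if it does not converge.
- **Usable phase.** Before analysis, set one minimum scan length per phase after motion removal, applied identically in both conditions.
- **Non-normality.** Keep the mixed model as primary, with the aligned-rank ANOVA on completers as a sensitivity analysis.
- **Reporting.** Tabulate early ends by condition, phase and reason.
- **Further sensitivity analyses.** The completer ANOVA, and a shift analysis that moves missing late-phase values in 0.1 SD steps until the conclusion changes.

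Cost: revised wording, one model in place of another, one table and some extra analyses. The late-phase result then relies on a missing-at-random assumption and, if the fallback is used, on its covariance form. No new data are needed and no clinical stopping rule changes.
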